8.3.10. Adverse Event Monitoring

All AEs (including AESIs during the treatment period) will be collected from the time of ICF signature until the EOT visit. From the EOT visit until the EOS visit, only SAEs and late onset AESIs will be collected.

Please refer to Section 9 for further details on AE collection.

8.5. Biological Specimen Collection

8.5.1. Estimated Volume of Blood Samples

For each participant enrolled, the estimated volumes of biological specimens collected during the study is listed in Table 8-4.

Table 8-4 Biological specimens collected during the study

Sample type	Type of assessment	Volume/Size
Blood/plasma	Hematology, biochemistry, pharmacokinetics, pharmacogenetics	180 mL

8.6. Health-Related Quality of Life Assessments

HRQL data will be collected to investigate the effects of xevinapant + CRT on participants' reported well-being compared to placebo + CRT.

The EORTC QLQ-C30 version 3.0, the EORTC QLQ-HN35 will be administered electronically:

- The EORTC QLQ-C30 questionnaire captures QoL dimensions that are relevant for oncologic participants independently of the cancer type.
- The EORTC QLQ-HN35 is a disease-specific supplementary module designed to capture dimensions that affect the QoL of head and neck cancer participants.

Further details on the questionnaires are provided in Appendix 13.4.

Administration of the HRQL questionnaires

EORTC QLQ-HN35 and EORTC QLQ-C30 questionnaires will be administered according to the schedule shown in Table 1-1 and Table 1-2 The participant should also complete the EORTC questionnaires at the time of progression.

The baseline HRQL assessment should be performed prior to randomization.

Questionnaires should be completed by participants prior to any clinical tumor assessment and/or receiving results of any test, including disease status. Particular attention should be devoted to maximizing compliance.

A nominated person in each center must be assigned to take responsibility for administration of HRQL forms. Participants should receive a short electronic training at screening, before completing the questionnaires. Participants should complete the questionnaires in a quiet, private area and any form of influence on their answers (e.g., conferring with friends, relatives, study personnel) should be avoided in order to ensure participant's privacy and absence of bias.

Completion of all 3 questionnaires is expected to take less than 25 minutes in total.

9. ADVERSE EVENTS

The Principal Investigator is responsible for ensuring that all staff involved in the study is familiar with the content of this section.

Investigators will seek information on AEs at each safety evaluation. All AEs whether reported by the participant or noted by authorized study personnel, will be recorded in the participant's medical

record and on the AE CRF. Their nature, severity, duration, and treatment, together with the Investigator's opinion as to their relationship to the drug, will be recorded. The Investigator will also indicate how the signs of the condition evolved.

As needed, Sponsor may ask for copies of certain medical records (e.g. autopsy reports, supplemental lab reports, documents on medical history/concomitant medications, discharge letters), as supporting source documentation associated to AEs. All participant identifiers, except the participant number, will be redacted on these copies before submission to Sponsor.

9.1. Definitions and Assessment Criteria

9.1.1. Definition of Adverse Events

The ICH Guidelines for GCP E6 (R1) defines an AE as: Any untoward medical occurrence in a participant or clinical investigation participant administered a pharmaceutical product and which does not necessarily have a causal relationship with this treatment. An AE can therefore be any unfavorable and unintended sign (including an abnormal laboratory finding), symptom, or disease temporally associated with the use of a medicinal product, whether or not considered related to the medicinal product.

Thus, any new sign, symptom or disease, or any clinically significant worsening of an existing sign, symptom or disease compared to the condition at the first visit should be considered as an AE, except if considered as associated with the underlying disease (for more details, see the paragraph below "Events that do not meet the definition of an AE").

Any abnormal laboratory test results or other safety assessments such as ECG findings, vital sign measurements), including those that worsen from baseline, and assessed to be clinically significant in the medical and scientific judgment of the Investigator, should be reported as an AE. Abnormal laboratory values that require an intervention such as a treatment or a change in the study treatment should also be reported as an AE.

If clinical sequelae are associated with a laboratory abnormality, the diagnosis or medical condition should be reported (e.g., renal failure, hematuria) not the laboratory abnormality (e.g., elevated creatinine, urine red blood cell count increased).

Events that do not meet the definition of an AE include:

- Any clinically significant abnormal finding or other abnormal safety assessment that is associated with the underlying study disease, disease progression/recurrence unless judged by the Investigator to be more severe than expected for the participant's condition.
- Diagnostic testing and procedures: Testing and procedures should not be reported as AEs or SAEs, but rather the cause for the test or procedure should be reported. If a test or procedure is done to rule out a diagnosis, the sign or symptom leading to the test/procedure should be the event term, and the event term should only be updated to the diagnosis if/when the diagnosis is confirmed. Testing and procedures performed solely as screening measures should not be reported as AEs or SAEs.
- Anticipated day-to-day fluctuations of pre-existing disease(s) or condition(s) present or detected at the start of the study that do not worsen.
- Lack of efficacy is not considered as an AE.

9.1.2. Definition of Serious Adverse Events

An SAE is any AE that:

- · Results in death.
- Is immediately life-threatening.
- Requires inpatient hospitalization or prolongation of existing hospitalization.
- Results in persistent or significant disability/incapacity.
- Is a congenital anomaly/birth defect in offspring of the participant.
- Is an important medical event that may jeopardize the participant or may require medical intervention to prevent one of the outcomes listed above.

Medical or scientific judgment should be exercised in deciding whether or not expedited reporting is appropriate in this situation. Examples of medically important events are intensive treatment in an emergency department or at home for allergic bronchospasm, blood dyscrasias, or convulsions that do not result in hospitalizations; or development of drug dependency or drug abuse.

An important medical event is an event that may not result in death, be life-threatening, or require hospitalization but may be considered an SAE when, based on appropriate medical judgment, it may jeopardize the participant and may require medical or surgical intervention to prevent one of the outcomes listed in the definitions for SAEs.

Examples of such events are intensive treatment in an emergency room or at home for allergic bronchospasm, blood dyscrasia, or convulsions that do not result in hospitalization.

Note: Inpatient hospitalization is considered to have occurred if the participant has had to stay overnight at the hospital.

The criterion for prolongation of hospitalization is also defined as an extra night at the hospital than planned. Hospitalization may not constitute sufficient grounds to be considered as a SAE if it solely for the purpose of diagnostic tests (even if related to an AE).

Pre-planned hospitalization: A hospitalization planned before signing the ICF is not considered an SAE, but rather a therapeutic intervention. However, if an event occurs during the pre-planned hospitalization that prolongs the hospitalization or meets any other SAE criteria, the event will be considered an SAE. Surgeries or interventions that were under consideration, but not performed before signing the ICF, will not be considered serious if they are performed after signing the ICF for a condition that has not changed from its baseline level.

[figure not shown]
Social admissions: hospitalizations for social reasons, for example, solely for the administration of chemotherapy, or due to long travel distances are also not SAEs.

9.1.3. Definition of Adverse Events of Special Interest

An AESI is a noteworthy event of the particular study treatments (xevinapant/placebo, chemotherapy and IMRT) that can be appropriate to monitor closely. An AESI may be serious or non-serious and an AESI could include events that might be potential precursors or prodromal symptoms for more serious medical conditions in susceptible individuals.

The rapid reporting of AESIs allows ongoing surveillance of these events in order to characterize and understand them in association with the study treatment administration (xevinapant/placebo, chemotherapy and IMRT).

All AESIs during the treatment period should be recorded promptly in the eCRF. In addition, AESIs that are also SAEs should be reported to the Sponsor within 24 hours.

9.1.4. Definition of Adverse Event Reporting Period

All AEs (including AESIs during treatment period) will be collected from the time of signature of ICF until the EOT visit. From the EOT visit until the EOS visit, only SAEs and late onset AESIs will be collected.

9.1.5. Assessment of Relationship with Study Treatment(s)

The Investigator or designee will determine the relationship between the AE and each study treatment according to the guidance below.

Table 9-1 Causal Attribution Guidance

	Is the AE/SAE suspected to be caused by the study treatments (xevinapant/placebo, chemotherapy, and IMRT) based on facts, evidence, science-based rationales, and clinical judgment?		
Reasonable causal relationship	causal chemotherapy and IMRT) makes a causal relationship possible, and other drugs, therapeutic interventions		
No reasonable causal relationship of the AE/SAE to study treatment administration (xevinapant/placebo, chemotherapy and IMRT) makes a causal relationship unlikely, or other drugs, therapeutic interventions or underlying conditions provide a sufficient explanation for the AE/SAE.			

Abbreviations: AE: adverse event; IMRT: intensity-modulated radiotherapy; SAE: serious adverse event.

The Investigator's assessment of causality for individual AE reports is part of the study documentation process.

Regardless of the "Yes" or "No" causality assessment for individual AE reports, Sponsor or designee will promptly evaluate all reported SAEs against cumulative product experience to identify and expeditiously communicate possible new safety findings to Investigators and applicable Regulatory Authorities.

9.1.6. Assessment of Severity of Adverse Events

AEs will be graded by the Investigator according to NCI-CTCAE, v5.0 criteria. The alternative definitions for grade 1, 2, 3, and 4 events mentioned in Table 9-2 should be used when the observed or reported AE is not in the NCI-CTCAE classification.

Table 9-2 Adverse Event Grading (Severity) Scale

Grade	Severity	Alternative Description
1	Mild	Awareness of sign or symptom, but easily tolerated; Transient or mild discomfort (<48 hours); no interference with the participant's daily activities; no medical intervention/therapy required.
2	Moderate	Discomfort enough to cause mild to moderate interference with normal daily activities; No or minimal medical intervention/therapy required.
3	Severe	Considerable interference with the participant's daily activities; medical intervention/therapy required; hospitalization possible.
4	Very severe, life- threatening or disabling	Extreme limitation in activity; significant medical intervention/therapy required, hospitalization probable.
5	Death related to adverse event	

9.2. Procedures for Recording Adverse Events

All AEs, whether expected or not, should be recorded immediately in the source document, and described on the AE form of the eCRF.

Investigators should use correct medical terminology/concepts when recording AEs or SAEs on the CRF. Avoid colloquialisms and abbreviations. There is one eCRF for recording AEs or SAEs. Only one medical concept should be recorded in the event field on the Adverse Event CRF.

9.2.1. Diagnosis Versus Signs and Symptoms

If known, a diagnosis should be recorded on the eCRF rather than individual signs and symptoms (e.g., record only liver failure or hepatitis rather than jaundice, asterixis, and elevated transaminases).

However, if a constellation of signs and/or symptoms cannot be medically characterized as a single diagnosis or syndrome at the time of reporting, each individual event should be recorded as an AE or SAE in the CRF. If it is an SAE, each individual event should be reported on a separate form. If a diagnosis is subsequently established, it should be reported as follow-up information.

9.2.2. Adverse Events Occurring Secondary to Other Events

In general, AEs occurring secondary to other events (e.g., cascade events or clinical sequelae) should be identified by their primary cause. For example, if severe diarrhea is known to have resulted in dehydration, it is sufficient to record only diarrhea as an AE or SAE in the CRF.

However, medically significant AEs occurring secondary to an initiating event that are separated in time should be recorded as independent events in the CRF. For example, if a severe gastrointestinal hemorrhage leads to renal failure, both events should be recorded separately on the CRF.

9.2.3. Persistent or Recurrent Adverse Events

A persistent AE is one that extends continuously, without resolution between participant evaluation time points. Such events should only be recorded once in the eCRF unless their severity increases. If a persistent AE becomes more severe, it should be recorded again on the Adverse Event CRF.

A recurrent AE is one that occurs and resolves between participant evaluation time points and subsequently recurs. All recurrent AEs should be recorded on the Adverse Event CRF.

9.2.4. Abnormal Laboratory Values

Only clinically significant laboratory abnormalities that require active management will be recorded as AEs or SAEs on the eCRF (e.g., abnormalities that require a treatment, study drug to be held or discontinued, more frequent follow-up assessments, further diagnostic investigation, etc.). If the clinically significant laboratory abnormality is a sign of a disease or syndrome (e.g., ALP and bilirubin 5 × the ULN associated with cholecystitis), only the diagnosis (e.g., cholecystitis) needs to be recorded on the Adverse Event CRF.

If the clinically significant laboratory abnormality is not a sign of a disease or syndrome, the abnormality itself should be recorded as an AE or SAE on the CRF. If the laboratory abnormality can be characterized by a precise clinical term, the clinical term should be recorded as the AE or SAE. For example, an elevated serum potassium level should be recorded as "hyperkalemia."

Observations of the same clinically significant laboratory abnormality from visit to visit should not be repeatedly recorded as AEs or SAEs on the CRF, unless their severity, seriousness, or etiology changes.

9.2.5. Deaths

All deaths occurring during the study will be reported on the death page of the eCRF.

Deaths that are attributed by the Investigator as solely due to disease progression (death due to cancer under study) are not considered as SAEs. Conversely, medical events leading to death should be reported as SAEs if they cannot be determined to be exclusively due to the progression of the cancer under study or if they do not correspond to the expected pattern of progression of the disease under study.

All other deaths are considered SAEs. They will be recorded on both the Death and SAE page of the eCRF:

- The SAE verbatim term of the event or condition that caused or contributed to the fatal outcome should be recorded as a single medical concept.
- If the cause of death is unknown and cannot be ascertained at the time of reporting, the verbatim term "Unexplained Death" should be recorded.
- The Investigator must notify all other deaths within 24 hours of awareness (refer to Section 9.3).

9.3. Procedure for Reporting Serious Adverse Events to the Sponsor

Notification of SAEs until the EOS visit will not depend on their relationship with study treatments: all SAEs and Serious Adverse Reactions (SARs) will be recorded until the EOS visit or until the study discontinuation/termination, whichever is the latest.

The Investigator must notify the Sponsor of all SAEs within 24 hours of awareness by completing the AE form provided in the eCRF. Once the AE is selected as a SAE and the form is saved in the eCRF, an email notification will be sent automatically to the Sponsor's Pharmacovigilance department. If for any reason the eCRF is not available, as a backup option, the SAE can be declared by email at [contact] using the paper "SAE report form".

If for any reason, the eCRF and email are not available, the paper "SAE report form" can be sent by fax to [contact] with the provided fax cover page entitled "Serious Adverse Event Report transmittal form".

Email and fax reporting should be followed by the completion of the AE form in the eCRF as soon as possible.

The processes are fully described in separate guidelines and will be provided to Investigators with the protocol.

9.3.1. Follow-up of Serious Adverse Events

All SAEs, regardless of severity, must be followed up:

• To resolution (the participant's health has returned to the baseline status or all variables have returned to normal),

or

 Until stabilization of the event has occurred (the Investigator does not expect any further improvement or worsening of the event),

or

 Until the event is otherwise explained regardless of whether the participant is still participating in the study.

Some events, such as metastases, are often ongoing; however, once these events have been determined by the Investigator to be stable or chronic, he/she may consider the event to be resolved or resolved with sequelae.

The Investigator will notify the Sponsor of any follow-up information in the eCRF page within 24 hours of new information awareness.

Any AEs that are unresolved at the participant's last visit in the study are followed up by the Investigator for as long as medically indicated, but without further recording in the eCRF.

Sponsor or designee retains the right to request additional information for any participant with ongoing AE(s)/SAE(s) at the end of the study, if judged necessary.

9.3.2. Procedure for SAE Communication

If required by applicable local regulations, the Investigator will promptly notify the relevant IRB/IEC (in addition to the Sponsor) of any SAE (including post-study SAEs and follow-up information) that occurred at their site or was brought to their attention by the Sponsor. The Investigator will verify that the IRB/IEC acknowledges receipt of the notification.

In case of Suspected Unexpected Serious Adverse Reaction (SUSAR), unusual increase in the frequency of the severity of expected SAEs or new safety data which could have an impact on the overall expectedness of Serious Adverse Reaction or change in the safety profile of the study treatment(s) that require the informed consent to be updated, the Sponsor will prepare a safety report according to regulatory requirements relating to safety reporting.

This report will be communicated by the Sponsor to all Investigators involved in clinical studies with xevinapant.

9.4. Other Events Requiring Immediate Reporting

9.4.1. Overdose

For this study, an overdose is defined as follows:

- For xevinapant: any dose higher than 200 mg/day.
- For cisplatin: any dose higher than 100mg/m² per cycle.
- For carboplatin: any dose higher than AUC = 5 per cycle.

Appropriate supportive treatment should be provided if clinically indicated. In the event of overdose, the participant should be observed closely for signs of toxicity. Overdoses should be recorded as an AE.

Any AEs associated with an overdose should be recorded as separate AEs in addition of the AE "Overdose".

If an overdose on a Merck KGaA, Darmstadt, Germany investigational product (Debio-1143 or matched placebo) occurs during the course of the study, the Investigator or other site personnel must inform appropriate Sponsor representatives immediately and no later than 24 hours after becoming aware of the event.

The designated Sponsor representative works with the Investigator to ensure that all relevant information is provided to the Sponsor's participant safety data entry site.

For overdoses associated with an SAE, the standard SAE reporting timelines apply.

For other overdoses, reporting must occur within 30 days.

9.4.2. Pregnancy

All pregnancies occurring from signing informed consent until 9-months visit should be reported to Merck KGaA, Darmstadt, Germany.

Pregnancy itself is not regarded as an adverse event unless there is a suspicion that the study treatment may have interfered with the effectiveness of a contraceptive method.

Congenital abnormalities/birth defects and spontaneous miscarriages should be reported and handled as SAEs.

Elective abortions without complications should not be handled as AEs.

Pregnancies should be followed up until the final outcome and documented event if the participant was discontinued from the study.

If any pregnancy occurs, the Investigator must:

- Discontinue study treatments (i.e., xevinapant/matched placebo, cisplatin/carboplatin and IMRT).
- Complete the pregnancy report form and send it within 24 hours of awareness by email at [contact] or by fax to [contact].

For the follow-up information, an updated pregnancy report form should be sent within 24 hours in the same way as the initial notification.

Any serious outcomes experienced by the parent and/or the fetus/child should be reported as SAEs using the SAE report form.

This procedure applies to pregnancies in female participants as well to those in female partners of male participants. Information on the pregnancy of a participant's partner must be obtained directly from the participant's partner. Therefore, prior to obtaining information about the pregnancy, the Investigator must obtain the consent of the participant's partner.

[figure not shown]

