Women of childbearing potential must agree to use highly effective contraceptive method(s) (see Section 8.1.3) from ICF signature to 6 months after the last administration of chemotherapy or 3 months after last dose of xevinapant/matched placebo, whichever is the latest.

Non-sterilized males who are sexually active with a female partner of childbearing potential must agree to use condom and spermicide from ICF signature to 6 months after the last administration of chemotherapy or 3 months after the last dose of xevinapant/matched placebo, whichever is the latest. Because male condom and spermicide is not a highly effective contraception method, it is strongly recommended that female partners of a male study participant use highly effective contraceptive method(s) (see Section 8.1.3) throughout this period.

Male participants must refrain from donating sperm during the clinical study and for 6 months after the last administration of chemotherapy or 3 months after the last dose of xevinapant/matched placebo, whichever is the latest. If not done previously, cryopreservation of sperm prior to receiving chemotherapy or xevinapant/matched placebo is advised to male participants with a desire to have children.

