Serum pregnancy test (β -HCG) will be conducted during screening by a central laboratory in women of childbearing potential (see Table 8-2). On C1D1, negative serum pregnancy status should be rechecked locally by serum or urine test only if the previous central laboratory result is older than 7 days. After C1D1, serum or urine tests should be performed locally according to schedule presented in Table 1-1 and Table 1-2

Should a pregnancy still occur, all study treatments should be discontinued immediately.

The Sponsor should be notified of any pregnancy that occurs in female participants or partners of male participants during participation in studies with xevinapant by submitting a specific pregnancy form. Any reports of pregnancy in participants or partners of participants will be followed up as described in Section 9.4.2.

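### Protocol Section 9.4.2 leaves it unclear whether a partner's pregnancy stops a male participant's chemoradiotherapy

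*Protocol*

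**What the plan says.** Four places in the protocol bear on this.

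- **Section 9.4.2.** Under "If any pregnancy occurs, the Investigator must" there are two bullets. The first is "Discontinue study treatments (i.e., xevinapant/matched placebo, cisplatin/carboplatin and IMRT"). The second is to send the pregnancy report form within 24 hours. Text on updated forms and on serious outcomes follows. Then comes the scope sentence: "This procedure applies to pregnancies in female participants as well to those in female partners of male participants". The section closes on how information about a partner's pregnancy is obtained: "Therefore, prior to obtaining information about the pregnancy, the Investigator must obtain the consent of" the partner.
- **Heading of Section 9.4.** Section 9.4.2 falls under "Other Events Requiring Immediate Reporting".
- **Section 8.1.3.** After a paragraph on pregnancy testing in women of childbearing potential, it says: "Should a pregnancy still occur, all study treatments should be discontinued immediately". The next paragraph covers notifying the sponsor of pregnancies in participants and partners, and ends: "Any reports of pregnancy in participants or partners of participants will be followed up as described in Section 9.4.2".
- **Section 7.1.** The list of circumstances in which all study treatments must stop includes the single word pregnancy, without saying whose.

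**The concern.** The trigger in Section 9.4.2 is any pregnancy, the instruction is mandatory, and the scope sentence brings in partners without setting aside the stop step. A reader who takes the procedure to be everything listed would stop a man's radiotherapy, platinum and study drug because his partner is pregnant. He would have no medical reason to stop.

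What is at stake is the care of an individual patient. Protocol Section 2.2 describes treatment in this disease as given with curative intent, and Section 4.3 says that high-dose fractionated radiotherapy is needed for cure. Section 6.1.2.3.1 strongly discourages interrupting IMRT. SAP Section 10.2 counts less than 66.5 Gy, when not for a medical or safety reason, as a clinically important deviation. Whether a stop ordered by the protocol would be classed that way is open to argument. The listing does show the weight placed on completing radiotherapy.

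The situation can arise. Section 5.1 asks men for condom and spermicide and recommends highly effective contraception for the partner, giving this reason: "Because male condom and spermicide is not a highly effective contraception method". Section 8.1.3 is mixed. It first says that men with partners of childbearing potential must agree to highly effective measures, and then repeats the condom-and-spermicide wording.

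**Working it through.** No figure in the plan is in dispute. The check is whether any current text limits the stop step to the participant's own pregnancy.

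| Place | Stops treatment? | Says whose pregnancy? | Exempts partners? |
|---|---|---|---|
| 7.1 | Yes, mandatory | No | No |
| 8.1.3, stop sentence | Yes | No | No |
| 8.1.3, notification paragraph | No | Participants and partners | Sends both to 9.4.2 |
| 9.4.2, first bullet | Yes, mandatory | Any pregnancy | No |
| 9.4.2, scope sentence | Extends the procedure | Participants and partners | No |

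Section 8.1.3 does not settle the matter. Its notification paragraph treats partners as a reporting matter, but its cross-reference returns the reader to the section that holds the stop bullet. For a pregnant female participant the three sections agree.

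**Size for one man, only if a site followed the stop-treatment reading.** Inputs come from Protocol Section 6.1.2 and Table 1-1:

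- IMRT: 35 × 2 Gy = 70 Gy, five fractions a week.
- Cisplatin: 100 mg/m² on Days 2, 23 and 44, so 300 mg/m² in all.
- Xevinapant or placebo: 6 × 14 = 84 days, starting on Days 1, 22, 43, 64, 85 and 106, so the last dose is on Day 119.

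Assumptions: Day 1 is a Monday, nothing was missed earlier, and the stop comes before that day's dose. Fractions then fall on Days 1–5, 8–12 and so on to 43–47. Radiotherapy lost = 70 − 2 × fractions given.

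| Stop on | Fractions given | Gy lost | Cisplatin lost (mg/m²) | Study-drug days lost |
|---|---|---|---|---|
| Day 8 | 5 | 70 − 10 = 60 (86%) | 200 | 84 − 7 = 77 |
| Day 22 | 15 | 70 − 30 = 40 (57%) | 200 | 84 − 14 = 70 |
| Day 29 | 20 | 70 − 40 = 30 (43%) | 100 | 84 − 21 = 63 |
| Day 43 | 30 | 70 − 60 = 10 (14%) | 100 | 84 − 28 = 56 |
| Day 64 | 35 | 0 | 0 | 84 − 42 = 42 |

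Against the SAP's 66.5 Gy: 33 fractions give 66 Gy (below) and 34 give 68 Gy (above). Fraction 34 falls on Day 46, so any stop before it leaves the man below that figure.

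**The case against.** A reader might infer that the protocol states a rule that a man's treatment stops when his partner is pregnant. The documents do not support that much.

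- In Section 9.4.2 the scope sentence does not directly follow the stop bullet. The report form, the updated form and the reporting of serious outcomes in parent and child come between them, and the sentences after it concern the partner's information and consent. Under a heading about immediate reporting, the procedure reads naturally as the reporting procedure.
- The stop sentence in Section 8.1.3 follows directly on pregnancy tests in women. Partners enter only in the next paragraph, for notification and follow-up.
- In Section 7.1 the neighbouring items that concern a person, such as progression, consent and toxicity, concern the participant.
- The amendment history in Section 13.10, used here only as evidence of intent, discusses pregnancy as something that happens to a participant, who stays in survival follow-up.

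All of this stands as evidence of what was meant. It does not remove the ambiguity, because the text never says that the first bullet is outside the procedure or that partners are outside the stop rule.

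The dose losses also apply only if a site took the unintended reading, and nothing shows that sites would. The reporting window in Section 9.4.2 runs to the 9-month visit, well past planned radiotherapy (Day 47) and study drug (Day 119), so for much of it there is no treatment to stop.

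**Conclusion.** The point holds as a drafting ambiguity in a mandatory instruction. Section 9.4.2 permits two readings: reporting only, which is probably what was meant, and stopping the man's treatment. Nothing in Sections 7.1 or 8.1.3 rules out the second. Severity is minor.

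That no express exemption exists is certain from the text. That sites would act on the harmful reading is not shown and is not claimed. The documents give no frequency for partner pregnancy during treatment, and it is probably rare. If it happened during chemoradiotherapy and the site stopped treatment, the loss to that man could be large, as the table shows under its stated assumptions.

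A reader might also infer a threat to the trial's results. The documents do not support that. The SAP's estimands for EFS and OS count patients regardless of treatment discontinuation, and no effect on EFS, OS or power is claimed.

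**What to change.** Make one edit in three sections.

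1. **Section 9.4.2, first bullet:** begin it with *For a pregnancy in a female participant:* and keep the rest of the bullet.
2. **Section 9.4.2, scope sentence:** replace it with *The reporting and follow-up steps also apply to pregnancies in female partners of male participants; a partner's pregnancy alone is not a reason to discontinue the male participant's study treatment.* The word *alone* leaves the other stopping criteria in Section 7.1 in force.
3. **Section 9.4.2, consent sentence:** leave it unchanged. It requires consent before information is obtained from the partner. Making the whole reporting step depend on consent would hold up the initial 24-hour notification.
4. **Section 7.1:** change the item to *Pregnancy of the participant*.
5. **Section 8.1.3:** in the stop sentence, insert *of a participant* after the word pregnancy.

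The cost is a few words and a memo to sites. The rules for pregnant participants, the visits, the sample size and the analyses do not change.
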